2.2 Endpoints

Primary Endpoint

- Cumulative rate of any spontaneous abortion occurring on or before 12 weeks following oocyte retrieval in all subjects treated with PVR and undergoing fresh embryo transfer.
Note: spontaneous abortion is defined as two positive β -hCG tests occurring at least two days apart on or after 2 weeks post-oocyte retrieval, but followed by observation of any empty intrauterine gestational sac (blighted ovum), intrauterine gestation without a fetal heart beat, or absence of viable fetuses, as documented by transvaginal ultrasound (TVUS).

Secondary Endpoints

- Cumulative rate of spontaneous abortions determined at 6 and 10 weeks post-oocyte retrieval in all subjects treated with PVR.
- Cumulative rate of biochemical abortions determined at 6 and 10 weeks post-oocyte retrieval in all subjects treated with PVR. Biochemical abortion is defined as a positive β -hCG test at 2 weeks and 2 weeks + 3-4 days post-oocyte retrieval, but followed by no observed gestational sac on a later TVUS, or followed by a negative β -hCG test.
- Rate of ectopic and heterotopic pregnancies in all subjects treated with PVR following oocyte retrieval.
- Rate of abnormal findings in clinical laboratory tests and vital signs for all subjects treated with PVR.
- Frequency, intensity/grade, seriousness, and relatedness of adverse events (AEs) for all subjects treated with PVR.
- Frequency, intensity/grade of vaginal bleeding/spotting, vaginal hemorrhage, pain, vaginal infection, and vaginal irritation for all subjects treated with PVR.
- Frequency, intensity/grade, seriousness, and relatedness of AEs associated with vaginal and cervical abrasions and lesions and with vaginal adhesions for all subjects treated with PVR.
- Frequency and reason for PVR discontinuation.
- Positive β -hCG rate (positive serum β -hCG test) at 2 weeks and 2 weeks + 3-4 days post-oocyte retrieval in all subjects treated with PVR.
- Clinical pregnancy rate (TVUS showing at least 1 intrauterine gestational sac with fetal heart beat) at 6 and 10 weeks post-oocyte retrieval in all subjects treated with PVR.

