7.2.8 Pelvic Examination

A pelvic speculum examination will be performed at screening, Visits 4, 7P, 8, 9, and 10 to document the presence and grade (intensity) of any pain, irritation, abrasions, or lesions on the cervix or vagina, including the presence and grade (intensity) of any vaginal adhesions, using standardized criteria. An unscheduled pelvic speculum examination can be performed at the discretion of the Investigator for any visit with an AE reported by the subject for vaginal pain or irritation; the standardized criteria for establishing grade (intensity) are to be applied ([Appendix 2](#)). If any lesions or abrasions are found on the cervix or vagina or vaginal adhesions are noted, another examination will be performed 2-4 days later (each of these visits is to be documented as an unscheduled pelvic examination). Subjects will be followed until the lesions/abrasions or vaginal adhesions resolve or until the final assessment at the End-of-trial visit, whichever comes first. Vaginal adhesions observed can be surgically addressed based on the Investigator's judgement.

Any clinically significant finding will be reported as an AE ([section 8](#)). Results will be recorded in the subject's chart and eCRF.

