8.3.1 Vaginal Pain and Irritation

The criteria for the grading of AE's associated with vaginal pain and irritation is found in [Appendix 3](#). The mapping of these grades to intensity criteria is described above (section [8.3](#)). For clinical findings of pain and irritation during scheduled or unscheduled pelvic examinations the criteria for grading provided in [Appendix 2](#) will be applied.

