Appendix 2 Pelvic Examination, Grade, and Criteria

PARAMETER	INDIVIDUAL SIGNS/SYMPOMTS				
	GRADE 0 NORMAL	GRADE 1 MILD	GRADE 2 MODERATE	GRADE 3 SEVERE	GRADE 4 POTENTIALLY LIFE-THREATENING
Pain	None	Pain causing no or minimal inference with usual social & functional activities	Pain causing greater than minimal inference with usual social & functional activities or the need for non-narcotic medication	Pain causing inability to perform usual social & functional activities or the need for narcotic medication	Disabling pain causing inability to perform basic self-care functions OR hospitalization (other than emergency room visit) indicated
Dyspareunia (pain with sexual activity)	None	Pain causing no or minimal inference with sexual function	Pain causing greater than minimal inference with sexual function	NA	NA
Tenderness* (Specify Area: Vulvar/Perineum, Vagina, Cervix (including cervical motion tenderness), Uterus, Adnexae, Pelvic/Lower Abdominal, or Ovulatory)	None	Mild tenderness	Moderate tenderness	Severe tenderness	NA
GENITOURINARY IRRITATION - VULVA					
Vulvar/vaginal itching	None	Itching causing no, mild or moderate inference with usual social & functional activities	Itching causing inability to perform usual social & functional activities; may require intervention such as antihistamine or bathing to provide relief	NA	NA
Vulvar edema	None	Mild, non-pitting edema	Moderate, 1-2+ pitting edema	3+ pitting edema, severe enough to require urinary drainage, or weeping edema ± skin breakdown	NA

PARAMETER	INDIVIDUAL SIGNS/SYMPOMTS				
	GRADE 0 NORMAL	GRADE 1 MILD	GRADE 2 MODERATE	GRADE 3 SEVERE	GRADE 4 POTENTIALLY LIFE-THREATENING
Vulvar erythema	None	Erythema covering <50% of vulvar surface	Erythema covering >50% of vulvar surface	NA	NA
Vulvar rash	None	Rash covering <50% of vulvar surface	Rash covering >50% of vulvar surface	Severe epithelial disruption with hospitalization indicated	NA
Bartholin's or Skene's gland	No findings	Cyst with no inflammation	Cyst or abscess with outpatient intervention indicated	Cyst or abscess with hospitalization indicated	Necrotizing fasciitis from Bartholin's abscess
GENITOURINARY LESIONS - VULVA					
Vulvar lesions (findings seen only by colposcopy should not be included here)	Normal variants including skin tags, moles, scars, etc.	Blisters, ulcerations, or pustules – no treatment indicated	Blisters, ulcerations, or pustules, with treatment indicated	Severe epithelial disruption with hospitalization indicated	NA

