VAGINAL ADHESIONS – VAGINA					
Vaginal Adhesion	None	Asympotomatic, manual removal of ring possible	Symptomatic (eg. irritation reported by patient), manual removal of ring possible	Surgical intervention (eg. adhesiolysis) required to resolve	Potentially life threatening; urgent intervention indicated.

* If both pain and tenderness are present, only report the one with the most severe grade

Note: Any finding deemed clinically significant after initiation of treatment is to be reported as an AE.

Adapted from: Division of AIDS Table for Grading the Severity of Adult and Pediatric Adverse Events, Addendum 1 (Female Genital Grading Table for Use In Microbicide Studies); November 2007.

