#### **10.4.3 Pelvic Examination**

A pelvic examination will be performed at screening, Visits 4, 7P, 8, 9, and 10 to document the presence and grade (intensity) of any pain, irritation, abrasions, or lesions on the cervix or vagina using standardized criteria, and the presence and grade (intensity) of any vaginal adhesions using standardized criteria. If any lesions or abrasions are found on the cervix or vagina or vaginal adhesions are noted, another examination will be performed 2-4 days later. The grade (intensity) for each type of assessment will be summarized by visit for the safety cohort. Furthermore, a shift table will be presented summarizing the change in grade (intensity) from Visit 4 to the End-of-trial, where the End-of-trial is defined to be the last assessment in the treatment phase.

An associated listing will also be produced.

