**Preferred terms associated with adverse events of special interest**

Vulvovaginal pain

Dyspareunia

Vulvovaginal discomfort

Vulvovaginal pruritus
Vulval oedema
Vulvovaginal erythema
Vulvovaginal rash
Bartholin's cyst
Urethral cyst
Vulval disorder
Vaginal oedema
Vulvovaginal dryness
Vaginal discharge
Vaginal erosion
Vaginal lesion
Cervix oedema
Cervical friability
Cervix erythema
Cervical discharge
Cervix disorder
Vulvovaginal adhesion
Vaginal haemorrhage
Vaginal infection
Uterine cervical erosion

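### The Appendix 2 footnote can drop grade 1 or 2 pain from a pelvic examination when tenderness is graded worse, and it gives no rule for ties

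*Protocol*

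**What the plan says.** - **Protocol Appendix 2** grades pain and tenderness in separate rows. Pain runs from grade 1 to grade 4 and is graded by interference with activities or need for medication. Tenderness is graded only as mild, moderate or severe. Its top category is "Severe tenderness" at grade 3, and grade 4 is marked not applicable. The tenderness row carries an asterisk that leads to the footnote: "If both pain and tenderness are present, only report the one with the most severe grade".
- **Protocol 7.2.8** states that the pelvic examination is done "to document the presence and grade (intensity) of any pain, irritation, abrasions, or lesions on the cervix or vagina".
- **Protocol 8.3.1** gives two grading routes. For adverse events: "The criteria for the grading of AE's associated with vaginal pain and irritation is found in" Appendix 3, which has no tenderness row and no such footnote. For examinations: "For clinical findings of pain and irritation during scheduled or unscheduled pelvic examinations the criteria for grading provided in" Appendix 2 apply.
- **Protocol 9.9.7 and SAP 10.4.3** plan the analysis: "The grade (intensity) for each type of assessment will be summarized by visit for the safety cohort". A shift table from Visit 4 to the last treatment-phase assessment is added. Neither section mentions the footnote or says how a grade withheld under it is coded.
- **Protocol 2.2** lists as a secondary endpoint: "Frequency, intensity/grade of vaginal bleeding/spotting, vaginal hemorrhage, pain, vaginal infection, and vaginal irritation for all subjects treated with PVR". Tenderness is not named there.
- **SAP 10.2.3 and Appendix 3** select special-interest adverse events by preferred term. The list includes "Vulvovaginal pain", dyspareunia and vulvovaginal discomfort, but no term that names tenderness.

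**The concern.** One instruction asks the site for the grade of any pain found. The other tells it to withhold that grade when tenderness is worse. A site that follows the footnote to the letter leaves no pain grade for that woman at that visit, and the SAP does not say whether the gap counts as grade 0 or as missing.

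Two descriptive outputs depend on this. The by-visit summary of examination pain can come out too low. The shift table can err either way: pain withheld at Visit 4 lowers the baseline, so later pain looks new or worse, while pain withheld at the last assessment makes earlier pain look resolved.

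The comparison is also between unlike scales, functional interference on one side and a bare severity word on the other. The tenderness row further covers sites such as the uterus, adnexae and lower abdomen, so tenderness outside the vagina can displace the pain grade.

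**Working it through.** The plan states no figure on this point, so there is none to reproduce. The check has three parts.

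**1. Which grades can be lost.** Inputs from Appendix 2: pain grade *p* = 1 to 4 and tenderness grade *t* = 1 to 3, which gives 4 × 3 = 12 pairs with both present. Rule: keep the higher grade.

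| Result under the footnote | Pairs (*p*, *t*) | Number |
|---|---|---|
| *t* > *p*: pain grade dropped | (1,2), (1,3), (2,3) | 3 |
| *t* = *p*: no rule | (1,1), (2,2), (3,3) | 3 |
| *p* > *t*: pain kept, tenderness dropped | (2,1), (3,1), (3,2), (4,1), (4,2), (4,3) | 6 |

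Only grade 1 or 2 pain can be lost to strictly worse tenderness. Grade 3 pain is at risk only in a tie. Grade 4 pain is never lost, because tenderness stops at grade 3. These are counts of possible pairs, not frequencies. In every row the higher of the two grades survives, ties included.

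**2. Effect on the examination pain count.** Let *q* be the share of women with pain at an examination and *s* the share of those with strictly worse tenderness. Then

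recorded share = *q* × (1 − *s*).

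Neither *q* nor *s* is in the documents. The values below are assumptions, applied to the planned 240 women of Protocol 9.2 for scale, with ties counted as pain kept.

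| *q* | *s* | True count, 240*q* | Recorded, 240*q*(1 − *s*) |
|---|---|---|---|
| 5% | 25% | 12 | 9 |
| 10% | 10% | 24 | 21.6 |
| 10% | 25% | 24 | 18 |
| 10% | 50% | 24 | 12 |
| 20% | 25% | 48 | 36 |

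If the withheld grade is treated as missing and leaves the denominator, the recorded share is *q*(1 − *s*)/(1 − *qs*). For *q* = 10% and *s* = 25% this is 0.075/0.975 = 7.7%, against 7.5% if it is coded as grade 0. Either way it is below 10%. For a given visit the error in the count goes in one direction only. Ties settled against pain would lower it further.

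**3. Which data the footnote reaches.** It stands only in Appendix 2, which Protocol 8.3.1 assigns to examination findings. Pain that the woman reports and the physician judges clinically significant becomes an adverse event (Protocol 3.1.2), graded under Appendix 3 without suppression. Examination pain not judged clinically significant has no adverse event route, so the examination table is its only planned record.

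**The case against.** The strongest reply is that the pain endpoint is mainly an adverse event endpoint. Protocol 3.5.2 places pain among the special-interest adverse events, and the table in SAP 10.2.3 is built from adverse events. A reader might infer from the footnote that the secondary endpoint of pain is under-counted by rule. The documents do not support that: a woman whose examination pain is withheld can still be counted through an Appendix 3 adverse event. This part of the reply stands.

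Second, the word *report* may refer to adverse event entry only, since the note directly below the footnote uses it in that sense. Both grades would then still be documented at the examination, the by-visit and shift tables would be intact, and the footnote would merely prevent double entry. This is a possible reading, but nothing in the protocol settles it, and sites may differ.

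Third, SAP 10.4.3 speaks of types of assessment, not table rows. If pain and tenderness were one type, keeping the worse grade would give a valid worst-grade summary and lose no woman. Neither document says that the rows are combined, and the list of what the examination covers does not name tenderness.

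Fourth, some inferences go beyond the text. The eCRF is not in the documents, so it cannot be said that a dropped grade is recorded nowhere. No rate shows that tenderness commonly masks pain at Visit 4, although that visit falls the day after retrieval. Whether an event entered as tenderness would miss the special-interest table depends on how it is coded.

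Last, these are descriptive summaries in a single-arm trial. No test or decision rule rests on pain.

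**Conclusion.** The point holds for pelvic examination data. On a literal reading the footnote contradicts Protocol 7.2.8, drops grade 1 or 2 pain in three grade pairs, leaves three ties undefined, and can lower by-visit examination pain counts and distort the shift table in either direction. It does not suppress pain adverse events graded under Appendix 3, never removes grade 4 pain, and does not touch the primary analysis, sample size or power.

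The size cannot be derived from the documents. The counts in the second table show how the effect scales with assumed values and are not estimates. The conclusion rests on *report* covering the examination record and on pain being tabulated apart from tenderness. If either fails, the examination tables lose no woman, and what remains is unclear wording, with the tie rule and the coding of tenderness events still open.

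**What to change.** 1. **Protocol Appendix 2.** Replace the footnote with: *Record the grade of both pain and tenderness at every examination; if both arise from the same event, enter one AE with the more severe grade (if equal, enter it as pain).* This is harmless under either reading of the present text and still prevents double entry.
2. **SAP 10.4.3.** Summarise pain and tenderness separately, and also as *pain or tenderness, worst grade*. For data already collected under the present footnote, show the worst-grade summary, which the rule preserves, and label the separate pain row as incomplete. This matters because Protocol 3.1.3 expects the last visit in Q3 2019 and the SAP refers to a protocol version dated 9 August 2019.
3. **SAP 10.2.3 and Appendix 3.** Ensure that adverse events entered as vulvar, vaginal or cervical tenderness are included in the special-interest table. The one-AE rule in item 1 does not secure this by itself.

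Cost: one footnote, an eCRF completion note, one extra table row and a check of the preferred-term list.

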Appendix 3 Assessment of AEs of Special Interest: Vaginal Pain and Vaginal Irritation

[figure not shown]
INDIVIDUAL SIGNS/SYMPOTOMS				
PARAMETER	GRADE 1 MILD	GRADE 2 MODERATE	GRADE 3 SEVERE	GRADE 4 POTENTIALLY LIFE- THREATENING
VAGINAL PAIN				
Pain	Pain causing no or minimal inference with usual social & functional activities	Pain causing greater than minimal inference with usual social & functional activities or the need for non-narcotic medication	Pain causing inability to perform usual social & functional activities or the need for narcotic medication	Disabling pain causing inability to perform basic self-care functions OR hospitalization (other than emergency room visit) indicated
Dyspareunia (pain with sexual activity)	Pain causing no or minimal inference with sexual function	Pain causing greater than minimal inference with sexual function	NA	NA
VAGINAL IRRITATION				
Vaginal itching	Itching causing no, mild or moderate inference with usual social & functional activities	Itching causing inability to perform usual social & functional activities; may require intervention such as antihistamine or bathing to provide relief	NA	NA
Vaginal dryness	Dryness causing no or minimal inference with usual sexual, social & functional activities	Dryness causing greater than minimal inference with usual sexual, social & functional activities	NA	NA
Vaginal discharge by participant report	Mild-moderate increase in amount above participant baseline – no sanitary protection required	Profuse increase in discharge requiring pad use or other hygienic intervention	NA	NA

Adapted from: Division of AIDS Table for Grading the Severity of Adult and Pediatric Adverse Events, Addendum 1 (Female Genital Grading Table for Use In Microbicide Studies); November 2007.

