8.2.2 Recording of Adverse Events

The Investigator must record all AEs in the AE Log provided in each subject's eCRF with information about:

- AE description
- Date and time of onset (time can be omitted, if not applicable)
- Intensity
- Causal relationship to IMP
- Action taken to IMP
- Other action taken
- Date and time of outcome (time can be omitted, if not applicable)
- Outcome
- Seriousness.

Each of the items in the AE Log is described in detail in the following sections.

Adverse Event

AEs should be recorded as diagnoses, if available. If not, separate signs and symptoms should be recorded. One diagnosis/symptom should be entered per record.

If a subject suffers from the same AE more than once and the subject recovers in between the events, the AEs should be recorded separately. If an AE changes in intensity, a worst-case approach should be used when recording the event, i.e., the highest intensity and the longest duration of the event.¹

Note the following: a procedure is not an AE; the reason for conducting the procedure is. Hospitalization is not an AE; the reason for hospitalization is. Death is not an AE, but the cause of death is (an exception is sudden death of unknown cause, which is an AE).

¹ Exception: if an AE with onset before the first IMP administration (i.e., a pretreatment AE) worsens in intensity, this must be recorded as 2 separate events. The initial AE should be recorded with outcome "not recovered" and the date and time of outcome are when the intensity changed. The second AE should be recorded with date and time of onset when the intensity changed.

Date and Time of Onset

The date of onset is the date when the first sign(s) or symptom(s) were first noted. If the AE is an abnormal clinically significant laboratory test or outcome of an examination, the onset date is the date the sample was taken or the examination was performed.

Intensity

The intensity of an AE must be classified using the following 3-point scale:

Mild: Awareness of signs or symptoms, but no disruption of usual activity.

Moderate: Event sufficient to affect usual activity (disturbing).

Severe: Inability to work or perform usual activities (unacceptable).

The grading of AEs of special interest will be based on predefined criteria as discussed in section [8.3](#).

Causal Relationship to IMP

The possibility of whether the IMP caused the AE must be classified as one of the following:

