8.3 Adverse Events of Special Interest

Standardized criteria will be applied to some AEs of special interest to establish intensity/grade (see Section 8.2.2). Mapping of grade to intensity for these AEs is described below; additional details are provided in [Appendix 2](#) and [Appendix 3](#).

Grade 1: Mild

Grade 2: Moderate

Grade 3: Severe

Grade 4: Potentially Life-Threatening

Any finding of grade 4 will be designated as an SAE.

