#### 10.2.1 Overview of Treatment-Emergent Adverse Events

A TEAE overview summary table will be prepared including the number of subjects reporting a TEAE, the percentage of subjects (%) with a TEAE, and the number of events (E) reported, for the following categories:

- Treatment-emergent adverse events
- Treatment-emergent Deaths
- Treatment-emergent Serious adverse events
- Treatment-emergent adverse events leading to withdrawal
- Treatment-emergent severe adverse events
- Treatment-emergent Adverse drug reactions

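### Protocol 8.2.2, 8.3 and Appendix 3 conflict on the intensity of vaginal irritation, so a Severe count of zero for itching, dryness, discharge, vaginal edema or vaginal erythema is fixed in advance.

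*Protocol*

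**What the plan says.** Protocol 8.2.2 sets a three-point intensity scale for all adverse events. Its top category reads "Severe: Inability to work or perform usual activities (unacceptable"; its middle category covers events that affect usual activity. The same section then makes an exception: "The grading of AEs of special interest will be based on predefined criteria as discussed in section" 8.3.

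Section 8.3 maps grade to intensity, including "Grade 2: Moderate", with Severe reserved for Grade 3. Section 8.3.1 sends vaginal pain and irritation events to Appendix 3, and irritation found at pelvic examination to Appendix 2.

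Appendix 3 has three irritation rows, all marked NA at Grades 3 and 4. Their highest entries, all Grade 2, are:

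- Itching: "Itching causing inability to perform usual social & functional activities; may require intervention such as antihistamine or bathing to provide relief"
- Dryness: "Dryness causing greater than minimal inference with usual sexual, social & functional activities"
- Participant-reported discharge: "Profuse increase in discharge requiring pad use or other hygienic intervention"

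In the pain row of the same table, Grade 3 is "Pain causing inability to perform usual social & functional activities or the need for narcotic medication".

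Protocol 9.9.2.1 and SAP 10.2.3 say that sites record the intensity of these events with the standardized criteria. SAP 10.2.1 has an overview row for "Treatment-emergent severe adverse events", and SAP 10.2.2 (like Protocol 9.9.2) tabulates treatment-emergent events by intensity. Neither treats events of special interest separately.

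**The concern.** The intensity or grade of vaginal irritation is a named secondary endpoint of a vaginal-ring safety trial with no control arm, so its tables will largely be read at face value. If one functional loss is Moderate for itching and Severe for pain or any ordinary adverse event, the pooled tables mix two meanings of Severe. A reader who sees no severe itching, dryness or discharge will take that as an observation about the ring, when the grading rules allowed no other result.

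**Working it through.** No sample size, power or event count is involved. The check sets the criteria side by side and counts rows.

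**Step 1: which scale applies.** 8.2.2 hands events of special interest to 8.3, 8.3.1 hands vaginal irritation events to Appendix 3, and 9.9.2.1 confirms that sites record intensity that way. The 8.2.2 event log has a single intensity item. The Appendix-based value is therefore the one that reaches the tables.

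**Step 2: the same effect on function under each rule.**

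| Effect on usual activities | 8.2.2 scale | Appendix 3 pain | Appendix 3 itching | Appendix 3 dryness |
|---|---|---|---|---|
| Moderate interference | Moderate | Grade 2, Moderate | Grade 1, Mild | Grade 2, Moderate |
| Activities prevented | Severe | Grade 3, Severe | Grade 2, Moderate | No cell above Grade 2, so Moderate |

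Itching sits one category lower than 8.2.2 at both levels. Dryness agrees at the middle level and is capped only at the top. Discharge is graded by amount and pad use, so it is capped but cannot be compared cell by cell with 8.2.2.

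**Step 3: irritation rows that stop at Grade 2.**

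- Appendix 3, vaginal irritation: 3 of 3.
- Appendix 2, vagina: 5 of 5 (edema, erythema, dryness, discharge by participant report, discharge seen by the clinician).
- Appendix 2, cervix: 3 of 3 (edema and friability, erythema, discharge).
- Appendix 2, vulva: 2 of 5 (vulvar/vaginal itching, vulvar erythema). Vulvar edema and vulvar rash reach Grade 3; Bartholin's or Skene's gland findings reach Grades 3 and 4.

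**Step 4: consequence.** Only Grade 3 maps to Severe. For vaginal itching, dryness, discharge, edema and erythema, the largest possible Severe count is 0 if sites follow the criteria. If n women had itching that prevented usual activities, 8.2.2 would give n Severe events; Appendix 3 gives n Moderate events and 0 Severe.

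**Step 5: where the two scales meet.** The severe-event row of SAP 10.2.1 and the by-intensity table of SAP 10.2.2 cover all treatment-emergent events, so they pool Appendix-derived intensities with 8.2.2 intensities. Neither document says that Severe is unavailable for some terms.

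**The case against.** The strongest reply is that this is a stated rule. 8.2.2 explicitly yields to the specific criteria, Protocol 1.2 says that adverse-event scoring was changed at the Agency's request, and both appendices are labelled as adapted from an external genital grading table. Whether the NA cells come from that table cannot be checked here. All of this may explain the Appendix grades. It does not explain why those grades are converted to intensity and pooled with a scale that gives the same functional loss a different label.

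The second reply is that little depends on it. The trial is descriptive and judged on all its safety information. No test, threshold or stopping rule uses severe irritation. Disruptive events remain visible through frequency, seriousness, discontinuations, causality tables and listings. That stands, and it limits the weight of the point.

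Two stronger readings are tempting, and the documents support neither:

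- A reader might infer that no severe irritation of any kind can appear. Vulvar edema and vulvar rash stand under an irritation heading in Appendix 2, can reach Grade 3, and have matching terms in the SAP Appendix 3 list. Vulvovaginal discomfort is on that list without an Appendix row. Because 8.3 applies standardized criteria only to some events of special interest, it may be graded on 8.2.2.
- A reader might count 4 of the 5 Appendix 3 rows as lowered, because dyspareunia also stops at Grade 2. Dyspareunia is classed there as pain and graded by sexual function. Only itching is clearly lowered at both levels, and even there interference between moderate and complete inability fits neither cell.

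**Conclusion.** The inconsistency is real and should be corrected. Itching is recorded one category below 8.2.2 at the two levels that can be compared. For vaginal itching, dryness, discharge, edema and erythema, a Severe count of 0 is built in, and the pooled tables do not say so.

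This assumes that sites apply the Appendix criteria as written and that the recorded intensity feeds the tables of SAP 10.2.1 and 10.2.2. The documents give no rate of severe irritation, so the number of misclassified events is unknown and may be small. Event frequency and seriousness are unaffected, and the documents give no ground for saying that the trial's overall safety conclusion would change.

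**What to change.** Reconcile 8.2.2, 8.3 and Appendix 3. Keep the Appendix 2/3 grade for the special-interest table in SAP 10.2.3. Also record the 8.2.2 intensity for events of special interest, and state in SAP 10.2.1 and 10.2.2 that the severe-event row and the by-intensity table use the 8.2.2 intensity for all events.

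Timing matters. Protocol 3.1.3 estimates the last visit in Q3 2019, and the current protocol and SAP are both dated 9 August 2019, so a new item may come near the end of follow-up and require retrospective grading. If a second intensity can no longer be collected, state in the SAP and on those tables that no Severe category exists for the capped terms and that itching preventing usual activities is counted as Moderate. That needs no new data and keeps the zero from being read as an observed one.

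The full fix costs one more eCRF item and a sentence each in 8.3 and the SAP. Some events would carry two intensities, which may differ, and a few irritation events may be reported one category higher.
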